## **A Prospective, Randomized Trial of the Effect of Buprenorphine Continuation versus Dose reduction on Pain Control and Post-Operative Opioid Use**

**Version Date: 5/12/2022**

**PI: [name].**

### **Introduction**

Buprenorphine is a high-affinity, partial mu opioid receptor agonist that is effective, life-saving opioid maintenance treatment (OMT) for individuals with opioid use disorder (OUD). Due to the pharmacokinetics of buprenorphine, managing acute post-surgical pain can be challenging, especially when full mu opioid receptor agonists are used concomitantly. Currently, the Substance Abuse and Mental Health Services Administration (SAMHSA)- the national organization that provides guidance on the management of substance use disorder treatment- recommends discontinuation of buprenorphine prior to surgery, replacing it with full opioid agonists for withdrawal prevention, to facilitate postoperative analgesia. However, SAMHSA states as an advisory warning that this can introduce significant risks to an individual's substance use recovery, including cravings and relapse. Conversely, SAMHSA also recommends full dose buprenorphine continuation perioperatively; however, they also warn that the risks associated with this management strategy include ineffective analgesia necessitating escalating opioid administration.

Preliminary clinical observations support that buprenorphine continuation at low analgesic doses (8mg) can adequately facilitate postoperative pain management without interrupting OUD treatment. Over the past couple of years, there has been growing support for perioperative continuation of buprenorphine. At our institution, providers are currently more willing to recommend low dose buprenorphine continuation, a significant practice shift from a year prior when buprenorphine discontinuation was the accepted standard. Furthermore, there are recent reviews- based on professional opinion as opposed to prospective studies- that contend buprenorphine should be continued without dose adjustment perioperatively. This is paradoxical to the reports saturating the literature up until recently asserting that patients had poorly controlled postoperative pain when maintained on high doses of

buprenorphine, leading to increased opioid utilization and disruption of hospital courses.

To date, no prospective trial has investigated low dose buprenorphine continuation in comparison to buprenorphine discontinuation and SAMHSA has not endorsed low dose buprenorphine continuation as a management strategy. Similarly, no study has compared full dose buprenorphine continuation to buprenorphine dose reduction perioperatively. Because of this, there has been a call for prospective studies to investigate an optimal perioperative buprenorphine dosing strategy. Since there is growing acceptance that the risks of OUD relapse with buprenorphine discontinuation overshadow the risks of increased opioid utilization and potentially difficult pain control with buprenorphine continuation, our next course of action is to determine whether full dose buprenorphine continuation is superior to reducing buprenorphine to analgesic doses in individuals with OUD presenting for elective surgery. For this study, we propose to compare postoperative pain scores, opioid consumption, outpatient opioid dispensing, and OUD related symptoms between these two treatment strategies. The goal of our study is to inform the development of guidelines for the perioperative management of patients on buprenorphine that are based on science as opposed to expert opinion.

## Background

Opioid use disorder (OUD) is a chronic neurobehavioral disease characterized by continued opioid use despite the desire to quit, often punctuated by cycles of remission and opioid use relapse. OUD is associated with high rates of medical comorbidity and life expectancy is two decades shorter when compared to those without OUD. In the past 20 years, opioid related deaths have risen exponentially. Maine has been especially devastated by this trend and, although OUD mortality rates declined in 2018, they are beginning to re-ascend. It is projected that the overdose death rates for 2020 will be the highest on record, as the first quarter of this year has seen a 23% increase in opioid related mortality. Unfortunately, despite our national crisis, opioids remain prominent in perioperative

analgesic regimens for the millions of surgeries and procedures performed each year in the United States.

Opioid maintenance therapy (OMT) with buprenorphine has reduced hospitalization rates and mortality for those with OUD. The optimal duration of OMT has not been established and relapse rates can be high when OMT is discontinued. A multi-site study sponsored by the National Institute on Drug Abuse (NIDA) reported relapse rates approaching 90% following the premature discontinuation of OMT.

Clinical opinion is mixed on whether buprenorphine should be held, continued at full dose, or reduced in the perioperative period as it is limited to case reports, case series and provider opinion. Acute post-surgical pain management can be challenging in these patients when standard pain regimens, including full mu opioid receptor agonists, are needed for post-operative pain management.

Buprenorphine has high receptor binding affinity, a long half-life, and displays partial mu opioid receptor agonism- all properties which can prevent effective analgesia from full mu opioid agonists used in conjunction for pain control.

Therapeutic doses of buprenorphine for OUD treatment (16-32mg) are thought to saturate opioid receptors, rendering further opioid use for analgesia ineffective.

There are published reports of patients with poorly controlled postoperative pain when buprenorphine was continued and some providers recommend buprenorphine discontinuation at about 72 hours prior to elective surgery and replacement with low dose opioid agonists to reduce the risk of opioid withdrawal.

There are preclinical data and evidence from patients taking buprenorphine for chronic pain at analgesic doses that the addition of opioid agonists is effective in treating breakthrough pain. Neuroimaging of opioid receptor availability in heroin dependent patients receiving buprenorphine suggest that 8mg of buprenorphine is the ideal dose where receptors are available for additional opioid agonists to bind and facilitate analgesia. We compiled this evidence to establish institutional guidelines to continue buprenorphine at an 8mg analgesic dose. We subsequently published a retrospective observational study about our experience with analgesic dosed buprenorphine continuation compared to discontinuation. We identified that outpatient opioid dispensing and PACU pain scores were significantly higher in the cohort where buprenorphine was discontinued compared to when it was continued. A recent retrospective study from Stanford University published similar findings, reporting that patients continued on buprenorphine perioperatively at varied tapered doses received significantly less opioid prescriptions without changes in pain scores when compared to patients where buprenorphine was discontinued. These clinical observations challenge previous assumptions that, due to its pharmacology, buprenorphine interferes with opioid based pain management. However, these studies are limited by their retrospective, non-randomized design, and their absence of controlled clinical conditions; also, they do not address relapse rates and postoperative OUD-related symptoms. Most importantly, current established

national guidelines are to continue buprenorphine without dose adjustment or to discontinue buprenorphine perioperatively, without evidence to support either strategy. The current national guidelines disclose that full dose buprenorphine continuation can lead to inability to treat pain with opioid agonists and discontinuation can lead to withdrawal, however, they do not include recommendation for adjusting buprenorphine to an analgesic dose to facilitate opioid based analgesia, while preventing withdrawal.

Even though no prospective trial has been conducted to identify if buprenorphine continuation or discontinuation should be the preferred strategy for perioperative pain management, in the past couple of years there has been a paradigm shift where many contend that the risks of OUD relapse with buprenorphine discontinuation outweigh the risks of increased opioid utilization and potentially difficult pain control with buprenorphine continuation. This is evident from our initial study, designed as a head-to-head comparison of buprenorphine continuation to discontinuation. In our two months of active recruitment for this study, we found a significant number of patients that were reluctant to enroll in the study. When given the option to stop versus continue their buprenorphine at a lowered dose, patients were understandably inclined to continue their buprenorphine at the lowered dose due to their concerns and fears of relapse. Also, many of the patients stated that their doctor told them to continue their buprenorphine- in line with the current MaineHealth guidelines of low dose continuation that the authors of this study proposal helped establish in 2020.

An outstanding question still remains regarding the optimal dosing of buprenorphine perioperatively. As stated previously, there is evidence to support that low dose buprenorphine continuation may be ideal, because when buprenorphine is at a lowered, analgesic dose, there would still be availability for full opioid agonists to work for pain control given increased opioid receptor availability. However, it is quite possible that even at elevated doses of buprenorphine and corresponding low opioid receptor availability, pain control is still possible and dose reduction is not required. Thus, we propose to compare full dose buprenorphine continuation to low dose buprenorphine continuation in

patients scheduled for elective surgery. It is worth noting that this revised proposal was intended to be our follow-up study upon completion of our prior study comparing buprenorphine continuation to discontinuation.

Our proposed study will provide data to improve acute pain management delivery for the growing population of individuals receiving buprenorphine as OUD therapy. Not only will our study address a considerable gap in care delivery, but it will help establish consensus for a topic that currently has mixed opinion. If this clinical trial identifies that buprenorphine dose reduction is no different than full dose buprenorphine continuation, than we can change our MaineHealth guidelines to recommend continuation without having to make any adjustments to patient's OUD treatment. If, however, we identify that patients with full buprenorphine continuation use more opioids and have prolonged hospital courses, it will confirm the need for our current guidelines, confirming our preliminary findings of adequate pain control with buprenorphine continuation at analgesic dosing. Additionally, it could help establish treatment plans where patients are provided with less opioids both as inpatients and outpatients decreasing opportunities for diversion and opioid related relapse. We will further explore the comprehensive effect of buprenorphine management strategies through engaging representatives from the substance use disorder community and the providers involved in the various phases of their care. Convening this group of stakeholders together as members of our Data Safety and Monitoring Review Board will help us identify the key concerns for patients with OUD. It will also allow us to tailor our study to address these issues, with the ultimate goal of reducing perioperative OUD severity and the risks associated with relapse.

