## **Hypothesis**

There is limited guidance on the optimal management of buprenorphine perioperatively and both buprenorphine discontinuation and continuation are acceptable standards of care. Buprenorphine continuation at low analgesic dosing is also accepted, however is not provided as a potential treatment strategy by SAMHSA. There is the risk of inadequate pain control necessitating opioid

escalation when buprenorphine is continued. Preliminary clinical observations support buprenorphine continuation at low analgesic doses (8mg) as it adequately facilitates postoperative pain management without interrupting OUD treatment, however to date, no prospective trial has investigated this treatment strategy in comparison to low dose buprenorphine continuation. Since optimal perioperative dosing strategies remain unknown, the purpose of this study is to investigate if buprenorphine continuation at analgesic dosing is superior to buprenorphine continuation in individuals presenting for elective surgery.

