### Specific Aims

**Aim 1:** To compare the efficacy of perioperative standard of care low dose buprenorphine continuation (STD-BUP) to full dose continuation (FULL-BUP) in adults maintained on buprenorphine for OUD. *Hypothesis 1: Postoperative pain scores at postoperative day (POD) 1 will be higher in FULL-BUP patients compared to STD-BUP patients and this difference will be clinically significant (defined as a > 20% difference in pain scores between groups).* We will measure pain using a numeric rating scale (NRS) of 0 to 10, a standard tool used in comparing analgesic efficacy between distinct treatment interventions.

**Aim 2:** To compare postoperative opioid consumption (excluding buprenorphine formulations) in adults maintained on buprenorphine for OUD, measured as morphine milligram equivalents (MME) at 24, 48 and 72 hours postoperatively. *Hypothesis 2: FULL-BUP patients will have higher opioid consumption at 24, 48 and 72-hours postoperatively compared to STD-BUP patients.*

**Aim 3:** To compare OUD symptom severity and depressive symptoms; measured preoperatively and 30 days postoperatively using the Patient Health Questionnaire-9 (PHQ-9), Current Opioid Misuse Measure (COMM), and Opioid Craving Scale (OCS) instruments. *Hypothesis 3: There will be no difference in OUD symptom severity and depressive scores FULL-BUP patients compared to STD-BUP patients, both on day of surgery and at 30 days postoperatively.*

**Aim 4:** To compare the number of opioid prescriptions and quantity (in MME) of opioid medications dispensed, up to 30 days following surgery. *Hypothesis 4: The number of opioid prescriptions and the quantity of MMEs dispensed will be higher*

*for FULL-BUP patients than for STD-BUP patients during the 30 day period following surgery.*

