## Significance

Greater than two million Americans are estimated to currently suffer from opioid use disorder (OUD), and over the past two decades, opioid related mortality has exponentially increased. Buprenorphine is a Food and Drug Administration (FDA) approved treatment for OUD management. Reflective of its long-term, life-saving benefits, buprenorphine is currently the most frequently prescribed medication in the state of Maine, with the blood pressure medication, hydralazine, being the second most commonly prescribed. Buprenorphine works by binding strongly to opioid receptors- targets for drugs of abuse - for relatively extended periods of time, attenuating the cravings and withdrawal symptoms that fuel opioid addiction and relapse. When individuals on buprenorphine present for surgery, their acute post-surgical pain can be challenging, as the opioid medications commonly given to provide analgesia are unable to easily displace buprenorphine. Currently, both buprenorphine discontinuation and continuation are recognized as acceptable standards of care. The Substance Abuse and Mental Health Services Administration (SAMHSA), the organization that manages the federal approval of buprenorphine prescribers, recommends either perioperative buprenorphine continuation or discontinuation, based upon patient and provider preference, with consideration of the inherent risks for each management strategy. However, there is limited specific guidance on the optimal perioperative management of buprenorphine in this patient population and low dose buprenorphine continuation is not currently described as a treatment option by SAMHSA .

Preliminary clinical observations support that buprenorphine continuation at low analgesic doses can adequately facilitate postoperative pain management without interrupting OUD treatment. However, no prospective trial has investigated this treatment strategy. The purpose of this study is to investigate whether buprenorphine continuation at analgesic dosing is superior to buprenorphine continuation in individuals presenting for elective surgery. Adults scheduled for

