elective surgery who are taking  $\geq 12$ mg buprenorphine for OUD treatment will be eligible for this study. Enrolled participants will be randomized to receive either a reduced analgesic dose of buprenorphine (8mg) or to continue buprenorphine on the day of surgery without dose reduction. Our primary outcome of interest is postoperative pain scores. Our secondary outcomes of interest are opioid consumption, opioid dispensing up to 30 days following the surgical procedure and OUD related symptoms, including opioid withdrawal, cravings and relapse. We hypothesize there will be a clinically significant increase in pain scores when buprenorphine is continued in full compared to when it is continued at a lower analgesic dose. We will define clinical significance as a difference in composite pain scores of greater than 20% between groups. We also hypothesize that opioid consumption and opioid dispensing will be greater with full dose buprenorphine continuation compared to low-dose continuation. This will be the first randomized trial comparing competing perioperative buprenorphine treatment strategies and will yield critical preliminary data for larger, confirmatory studies. Additionally, we envision that this study will lay groundwork for follow-up investigations in this patient population, focused on preventing opioid cravings and relapse perioperatively, along with other clinical scenarios where acute pain is anticipated, such as intensive care unit settings.

Successful execution of this prospective trial will provide [name] with the tools and critical experience necessary to pursue her aspirations of becoming a successful clinical investigator. [name] has a mentorship team that is committed to her success and is led by her department chair, [name]. Her mentorship team also includes [name], [name], [name], [name], [name] and [name]. Her mentorship team will help provide guidance as she mentors residents, including [name], that have expressed interest in engaging in clinical research. They will meet with her periodically and provide her with any feedback that is required, based upon the trial phase, to help promote successful trial completion.

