#### Measures for Aim 1 (Pain scores)

The primary outcome of this study will be composite pain scores 24 hours after surgery. Others have shown that composite pain scores quantify pain with greater accuracy than a single measurement. Jensen et. al. concluded in their study that composite pain intensity scores from two or more individual ratings of pain are valid for detecting treatment effects. Pain scores will be measured using a numeric rating scale (NRS) (0=no pain; 10= worst possible pain). "Worst," "average," and

“least” pain scores will be assessed for the preceding time interval at 24, 48, and 72 hours following surgery. Inpatient pain scores will be collected as part of routine post-operative care and will be extracted from the medical record; there is no set protocol for routine pain score collection but typically it is done every 4-8 hours. To collect pain scores, nursing staff asks patients to rate their current pain on a scale from 0-10. If a participant is discharged prior to 72 hours after surgery, NRS scores will be assessed at the remaining time points via telephone. Prior to discharge, study staff will provide patients with a log to keep a record of their pain scores, at least once every 8 hours, in order to mitigate recall bias in anticipation of being contacted by research staff. Study staff will call discharged patients and ask them to report their pain scores for each 24 hour period between discharge and 72 hours postoperatively as recorded on the forms they were given at time of discharge.

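### Background lets a no-difference result change the local guideline, but the available analysis text plans no confidence interval for the between-arm difference and no rule for reading a non-significant test

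*Combined protocol and SAP*

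**What the plan says.** The last paragraph of Background gives two uses of the result. On one side: "If this clinical trial identifies that buprenorphine dose reduction is no different than full dose buprenorphine continuation, than we can change our MaineHealth guidelines", the change being to continuation without adjusting the patient's OUD treatment. On the other side, the existing guideline would be confirmed if "patients with full buprenorphine continuation use more opioids and have prolonged hospital courses". The first sentence is permissive and names no outcome. The second names opioid use and hospital course, not pain.

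The trial is framed as superiority. Hypothesis gives its purpose as to "investigate if buprenorphine continuation at analgesic dosing is superior to buprenorphine continuation", and Significance repeats it. Under Measures for Aim 1, "The primary outcome of this study will be composite pain scores 24 hours after surgery". Hypothesis 1 predicts more pain in FULL-BUP. Hypothesis 3 predicts a null: "There will be no difference in OUD symptom severity and depressive scores".

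Biostatistical Analysis sizes the trial for a 20-point difference on a 0-100 scale, which it calls clinically significant. It then plans:

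- descriptive summaries (means with SD, medians with IQR, counts);
- two-sided t or Mann-Whitney tests between arms, with chi-square or Fisher tests for categorical data;
- paired tests and correlations;
- ANCOVA or mixed models to explore differences already observed.

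The interim rule stops only for a detected difference. Final significance is at 0.047. The available text mentions no confidence interval for the between-arm difference and does not say what a non-significant result means. The text between Biostatistical Analysis and Limitations was not available to us, so the absence is stated only for what we could read.

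**The concern.** The plan says how a difference will be declared. It does not say how the absence of one will be established, although Background attaches a possible guideline change to that absence. With only a p-value and per-arm summaries to go on, a reader could take p above 0.047 as the no-difference finding. A non-significant test is compatible with no effect, and it can also be compatible with an effect the protocol itself regards as clinically important. An interval for the difference separates these cases; per-arm means and SDs do not show it directly.

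At stake is whether an uninformative result could be cited for a change in perioperative guidance while a clinically significant increase in pain has not been ruled out. Hypothesis 3 has the same gap in weaker form, since no decision is attached to it.

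**Working it through.** **Inputs, all from Biostatistical Analysis:** SD 28; difference of interest 20 points (means 50 and 30); 32 per arm for analysis, 40 per arm enrolled; sample-size alpha 0.05; final level 0.047. **Assumptions:** the no-difference judgement is made on the 24-hour composite pain score, that score has SD 28, the arms are equal in size, and the interim look is ignored. Paired results are for 32 / 40 per arm.

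**1. The plan's own figure.** A two-sample t-test with difference 20, SD 28 and alpha 0.05 needs 32 per arm (exact noncentral-t power 80.3%). Adding 8 per arm gives 40 per arm and 80 in total. Both figures reproduce. At 0.047, power with 32 per arm is 79.5%.

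**2. Precision.** SE = SD × √(2/n) = 28 × √(2/32) = 7.00, and 28 × √(2/40) = 6.26. The interval matching 0.047 is a 95.3% CI:

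- half-width = t(1 − 0.047/2; 2n − 2) × SE
- n = 32: 2.027 × 7.00 = 14.2
- n = 40: 2.018 × 6.26 = 12.6

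**3. Which non-significant results leave 20 open.** An estimate d (FULL-BUP minus STD-BUP) is non-significant if |d| is below the half-width. It fails to exclude 20 if d + half-width is at least 20.

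- n = 32: from 20 − 14.2 = 5.8 up to 14.2 points
- n = 40: from 20 − 12.6 = 7.4 up to 12.6 points

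Non-significant estimates below 5.8 / 7.4 do exclude 20.

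**4. Two examples at SD 28.**

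| Observed difference | n per arm | p | 95.3% CI | Excludes 20? |
|---|---|---|---|---|
| 10 | 32 | 0.16 | −4.2 to 24.2 | no |
| 10 | 40 | 0.11 | −2.6 to 22.6 | no |
| 5 | 32 | 0.48 | −9.2 to 19.2 | yes |
| 5 | 40 | 0.43 | −7.6 to 17.6 | yes |

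All four are non-significant, yet they support different conclusions.

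**5. How often (simulation, SD estimated in each trial, 1,000,000 trials per case, SD 28).**

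- True difference 10: 72% / 66% of trials are non-significant, and 61% / 48% of those intervals include 20.
- True difference 0: 95.3% are non-significant, and 19% / 10% of those intervals include 20, so 81% / 90% exclude it.

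**6. Fitness of the design for the corrected reading.** By symmetry with step 1, the chance that the upper limit falls below 20 when the true difference is 0 equals the power to detect 20: 79.5% / 87.8% at the 0.047 level.

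**7. Sensitivity to SD (24 and 20 are assumed values).**

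| SD | Half-width | Non-significant but 20 not excluded |
|---|---|---|
| 28 | 14.2 / 12.6 | 5.8–14.2 / 7.4–12.6 |
| 24 | 12.2 / 10.8 | 7.8–12.2 / 9.2–10.8 |
| 20 | 10.1 / 9.0 | 9.9–10.1 / none |

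The zone closes when the half-width reaches 10, that is at SD = 10 / (t × √(2/n)) = 19.7 / 22.2.

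The documents give no SD for opioid use, hospital course or the Hypothesis 3 instruments, so no figure can be given for them.

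**The case against.** The strongest reply has several parts, and some of them stand.

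- **The sentence is Background rationale.** It says what could be done, not what will be done, and Significance describes the trial as yielding preliminary data for larger confirmatory studies. The protocol also treats buprenorphine continuation as an accepted standard and full-dose continuation as endorsed by SAMHSA, so the change would be between practices it already regards as acceptable. This lowers the severity. It does not remove the gap, because this sentence is where a use for a null result is stated.
- **The figures concern an outcome the sentence does not name.** True; they are conditional on 24-hour pain. SD 28 is reported for a mean NRS and not expressly for the composite, which could vary less. Step 7 shows that a small enough SD removes the problem.
- **Part of the document was not available.** True, and the claim is limited accordingly.
- **A competent analyst would report an interval anyway.** Probably. Prespecifying it still settles the level (95% or 95.3%), the estimator and the threshold before the data are seen.

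A reader might also infer two stronger points that the documents do not support. One is that every non-significant result here would be inconclusive: steps 3 and 5 show that small estimates exclude 20 points, as do most non-significant results when the arms truly do not differ. The other is that the trial is too small to read a null result: against the plan's own 20-point threshold, the planned size gives about 80% power to exclude it at a true difference of 0.

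**Conclusion.** The concern holds in this form. Background ties a possible guideline change to a no-difference finding, and the available analysis text offers only difference tests, with no interval for the difference and no rule for a null result. If the outcome is the 24-hour composite pain score and the SD is 28, non-significant estimates of about 5.8 to 14.2 points (32 per arm) or 7.4 to 12.6 points (40 per arm) do not exclude the plan's own clinically significant difference. Estimates below those ranges do, and the problem vanishes at an SD below about 19.7 or 22.2. The sample size stands.

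Severity is minor to moderate: the wording is permissive and the trial is described as preliminary, but the plan as written lets a missed superiority test be read as no difference.

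A separate, minor wording point: Hypothesis 1 sets clinical significance as "defined as a > 20% difference in pain scores between groups" without saying what the percentage is taken of, and Significance does the same. The 20/100 points in the sample-size text suggest 20% of the scale, and the sample size is consistent with that reading.

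**What to change.** 1. In Biostatistical Analysis, prespecify the FULL-BUP minus STD-BUP difference in the primary 24-hour pain score with a 95.3% CI, matching the final 0.047 level. Use the mean difference, or the Hodges-Lehmann shift if the Mann-Whitney test is used.
2. Add a reading rule, for example: *A non-significant test does not by itself show that the arms are no different. A clinically significant increase in pain with FULL-BUP is ruled out only if the upper confidence limit is below 20/100 points (2 NRS points); otherwise a non-significant result is inconclusive.*
3. In Background, name the outcome on which no difference will be judged and tie the sentence to that interval, or soften it.
4. Report the Hypothesis 3 outcomes with intervals for the between-arm differences, and do not claim no difference from p-values alone.

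The cost is a few sentences and one reported interval per comparison. Patients, visits, data, primary test and sample size are unchanged. The downside is that some null results will have to be reported as inconclusive.
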